## **Binary endpoints**

Binary secondary efficacy endpoints defined in Section 9.2.1 will be analyzed using logistic regression with treatment group as main effect and corresponding baseline value(s) as covariate. Missing values will be addressed using a multiple imputation approach which will be described in the SAP. The variables in the multiple imputation model will at least include the same variables as used in the logistic regression model. Treatment effects will be compared and the combined odds ratio estimate between the treatment groups, with their corresponding 97.5% CIs and p-value will be provided.

In the data dependent case that the logistic regression method is not applicable (eg, the response rate is zero in 1 treatment arm and thus the maximum likelihood estimate may not exist), the Last Observation Carried Forward (LOCF) approach would be used for handling of missing values and an exact conditional logistic regression would be performed to compare treatment effects. The LOCF imputation method will consist of using the last value obtained up to the Week 24 analysis window (or Week 12 as applicable) to impute the missing Week 24 value (or Week 12 respectively).

The same methodology will be applied to compare alirocumab versus fenofibrate in the "intent to prescribe fenofibrate" stratum.

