# Analysis in the fenofibrate stratum

A MMRM model will also be used to compare alirocumab versus fenofibrate with additional interactions terms: treatment group-by-stratum- and treatment group-by-stratum-by-visit. The model will be run with all patients, whatever their stratum and will be also used to derive the treatment effect in the other strata (Section 2.4.4.5). In case of non-convergence of the model with the triple interaction, the same model as the primary efficacy analysis will be run in the "intent to prescribe fenofibrate" stratum.

26-Apr-2017

The appropriate contrast statement will be used to test the difference between the estimate of alirocumab group and the estimate of usual care group in the fenofibrate stratum.

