## Sensitivity to randomization strata

In order to assess the robustness of the primary analysis to randomization stratum mistakes (i.e., the stratum recorded in IVRS differs from the actual one), the MMRM model will be re-run including the actual stratum as per the e-CRF instead of the stratum recorded in IVRS. The actual stratum as per the e-CRF is defined, for the patients randomized to usual care only, as the actual usual care treatment taken for the longer time. In case no additional LMT is recorded using e-CRF page "Usual Care Medication for Lipid Modification therapy", the actual stratum will be assigned to "no intent to prescribe an additional LMT".

Sensitivity to handling of missing data - Pattern mixture model

In order to assess the robustness of the primary efficacy analysis with regards to handling of missing data, a sensitivity analysis will be conducted based on a pattern-mixture model approach.

Multiple imputation will be used with different imputation strategies applied to non-HDL-C values missing during the on-treatment period (as defined below)

- Patients randomized to alirocumab would continue to show benefit from treatment similar to that observed at the scheduled time point within 21 days of their last dose of open-label alirocumab (on-treatment period). Therefore, non-HDL-C values missing during the ontreatment period (e.g., samples obtained outside the specified window, no blood sample available although visit was performed, etc) should be considered as "Missing At Random" and imputed using a model based on other on-treatment measurements, gender, age and BMI;
- Patients randomized to usual care with additional LMT would continue to show benefit from treatment similar to that observed at the scheduled time point within 3 days of their last dose of LMT. Therefore, non-HDL-C values missing during the on-treatment period (e.g., samples obtained outside the specified window, no blood sample available although visit was performed, etc) should be considered as "Missing At Random" and imputed using a model based on other on-treatment measurements, gender, age and BMI;
- Patients, randomized to usual care and for whom the Investigator has not prescribed an additional LMT, would tend to have non-HDL-C values similar to baseline. Therefore, non-HDL-C values missing after randomization should be imputed based on patient's own baseline value;

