- Patients who stopped taking their study treatment no longer benefited from it after discontinuation, and thus tended to have non-HDL-C values returning to baseline. Therefore, non-HDL-C values missing after on-treatment period should be imputed based on patient's own baseline value.

Missing non-HDL-C values will be imputed 100 times to generate 100 complete data sets. The percent change from baseline to Week 24 will be derived from observed and imputed non-HDL-C at this time point. The completed data sets will be analyzed using an ANCOVA model with treatment group and randomization stratum as per IVRS as fixed effects, and the baseline non-HDL-C value as continuous covariate. The results from the 100 analyses will be combined using Rubin's formulae (6).

26-Apr-2017

To assess the homogeneity of the treatment effect across various subgroups, treatment group-by-subgroup factor, time point-by-subgroup factor, and treatment goup-by-time point-by subgroup factor interaction terms and a subgroup factor term will be added as fixed factors in the primary MMRM model described in Section 2.4.4.1.1. LS means difference versus usual care at Week 24 will be provided, as well as the corresponding SE and 97.5% CI, within each subgroup. The

significance level of the treatment group-by-subgroup factor interaction term at Week 24 will be also provided for each factor for descriptive purpose. Forest plots will be provided.

For each subgroup analysis, subgroups will be included in the analysis only if there are ≥10

patients by subgroup and treatment arm. Otherwise, unless specified below, the subgroups not meeting the required number of patients will be pooled to form larger subgroups if possible, or they will be excluded from analysis.

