#### 2.4.4.2.2 Continuous endpoints anticipated to have a non-normal distribution

Continuous secondary efficacy endpoints defined in Section 2.1.3.2, anticipated to have a non-normal distribution (i.e., TG, TGRL, and Lp(a)); will be analyzed using a robust regression model (i.e., ROBUSTREG SAS procedure with M-estimation option) with treatment group, randomization stratum as per IVRS as main effects and corresponding baseline value(s) as covariate. Missing values will be addressed using a multiple imputation model. The imputation model will include:

- The variables included in the robust regression model, i.e. the treatment group, the randomization stratum, and the baseline value.
- The baseline characteristics such as: age, BMI, and gender. Age and BMI will be included as continuous variables.
- The values at Week 8, Week 12, Week 20 and Week 24 time points.

Non continuous variables included in the imputer's model (i.e., treatment group, randomization stratum, and gender) are not expected to be missing.

In the robust regression model, the analyzed endpoint at time point of interest will be derived from observed and imputed lipid values at this time point. The treatment group combined means will be provided with respective SE estimates. The combined mean difference between the treatment groups will be provided with the SE, 97.5% CI and p-value through the SAS MIANALYZE procedure.

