## 2.4.4.4 Multiplicity issues

In order to handle multiple key secondary efficacy endpoints (for both analyses, i.e. alirocumab versus usual care and alirocumab versus fenofibrate), the overall type-I error (0.025 for each analysis) will be controlled by the use of a sequential inferential approach. Statistical significance of the primary parameter at the 0.025 alpha level is required before drawing inferential conclusions about first key secondary parameter (refer to order in Section 2.1.3.2.1).

Inferential conclusions about successive key secondary efficacy parameters require statistical significance of the prior one. This fixed hierarchical approach will ensure a strong control of the overall type-I error rate at the 0.025 level for each analysis (alirocumab versus usual care and alirocumab versus fenofibrate).

No further adjustments will be made for other efficacy endpoints for which p-values will be provided for descriptive purpose only.

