#### 2.4.4.5 Additional efficacy analyses

All analyses of the efficacy endpoints (primary, key secondary and other efficacy endpoints) will also be performed within each other randomization stratum as per IVRS (no additional LMT, or intent to prescribe ezetimibe, omega-3 fatty acids, or nicotinic acid) in order to compare the efficacy of alirocumab versus the other options of usual care. The analyses will be similar to the ones performed for the fenofibrate stratum (see Section 2.4.4.1.1) provided that there are at least 10 patients in each treatment arm in the stratum of interest.

Additional efficacy analyses on selected endpoints will also be replicated in the subgroup of patients of the region North America.

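### Do the thinly specified imputation models, for the pattern-mixture analysis and for TGs and Lp(a) in the fenofibrate contrast, need to be rewritten?

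*SAP*

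**What the plan says.** **Pattern-mixture analysis (SAP 2.4.4.1.3).** On-treatment gaps in non-HDL-C are treated as missing at random and "imputed using a model based on other on-treatment measurements, gender, age and BMI". The instruction appears twice: once for alirocumab (within 21 days of the last dose) and once for usual care with an added LMT (within 3 days). Usual-care patients without an added LMT, and anyone past the on-treatment window, are imputed from their own baseline. The 100 completed data sets are analysed with an "ANCOVA model with treatment group and randomization stratum as per IVRS as fixed effects, and the baseline non-HDL-C value as continuous covariate".

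**TGs and Lp(a) (SAP 2.4.4.2.2).** The robust regression is specified "with treatment group, randomization stratum as per IVRS as main effects and corresponding baseline value(s) as covariate". The imputation model holds "The variables included in the robust regression model, i.e. the treatment group, the randomization stratum, and the baseline value", plus age, BMI, gender and the four visit values.

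**Fenofibrate contrast.** SAP 2.4.4 sends every efficacy endpoint through both comparisons. SAP 2.4.4.4 applies the fixed sequence "for both analyses, i.e. alirocumab versus usual care and alirocumab versus fenofibrate". The only fenofibrate model written out in the SAP is an MMRM with treatment-by-stratum terms (2.4.4.1.1): "The model will be run with all patients, whatever their stratum". For the remaining strata, SAP 2.4.4.5 points back to it: "The analyses will be similar to the ones performed for the fenofibrate stratum (see Section 2.4.4.1.1". Protocol 11.4.2.2 ends with the line "The same methodology will be applied to compare alirocumab versus fenofibrate in the" fenofibrate stratum.

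**The concern.** An imputation model should normally contain at least the variables of the analysis model. The pattern-mixture list lacks three of them (treatment, stratum, baseline), while the TG and Lp(a) list in the same SAP includes all three. If one pooled model were fitted without treatment, imputed values in the two arms would be drawn together. The resulting shrinkage would then be read as sensitivity to missing data, which is what this analysis is meant to measure.

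For TGs and Lp(a), a regression with treatment and stratum as main effects gives one common treatment effect and no fenofibrate-specific estimate. If the imputation were pooled in the same way, missing TG values in fenofibrate patients would be pulled toward the other usual-care options. These endpoints stand 6th and 7th of nine in a fixed sequence, so HDL-C and LDL particle number can be claimed against fenofibrate only after them. Two programmers could produce two different confirmatory results.

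**Working it through.** **1. What is confirmatory.** The protocol splits alpha as 0.025 + 0.025 = 0.05, so the fenofibrate tests on Lp(a) and TGs are confirmatory. The pattern-mixture analysis is a sensitivity analysis. The primary MMRM already contains baseline, stratum and their time interactions.

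**2. How the pattern-mixture text reads.** The two treated groups have separate bullets and different on-treatment windows, and usual care without an LMT has a third rule. That structure points to fitting by arm, which makes a treatment term unnecessary. Raw non-HDL-C is imputed and percent change is derived afterwards, so a patient's other on-treatment values already carry much of the baseline information.

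**3. Size for the pattern-mixture analysis.** The documents give no effects, SDs or missing rates, so all inputs are assumed:
- 280 and 140 patients. Strata none/fenofibrate/ezetimibe/omega-3/nicotinic acid at 20/30/30/15/5%.
- Percent change: alirocumab -37; usual care 0/-8/-15/-3/-10. The usual-care mean is 0.30(-8) + 0.30(-15) + 0.15(-3) + 0.05(-10) = -7.85, so the true difference is -37 + 7.85 = -29.15.
- Patients whose gaps fall under this model: 280 + 0.80 × 140 = 392. At 10% missing, about 39 are imputed.

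| Imputation, 5-20% missing | Shrinkage of the difference (points) |
|---|---|
| By arm, no baseline or stratum, missingness alike in both arms | about 0.1 or less |
| By arm, no baseline or stratum, missingness tied to baseline in usual care only | 0.1-0.5 (0.2-0.9 if only Week 8 is seen) |
| By arm, with baseline and stratum | about 0.1 or less |
| Pooled, no treatment term | 0.1-0.8 (0.3-1.8 if only Week 8 is seen) |

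Two further simulations agree. With a true difference of -30, SD 25 and 5-15% missing, adding baseline to a by-arm model changed the result by less than 0.1, and pooled fitting cost 0.1 to 1.5. With raw values imputed and a difference near -29, the by-arm omission cost less than 0.1, or 0.1 to 0.6 under one-sided missingness. Pooled fitting cost 0.2 to 1.9. These shifts are all toward zero, so they work against a claim of superiority.

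**4. How the fenofibrate text reads.** Protocol 11.4.2 and SAP 2.4.4 include all efficacy endpoints in the fenofibrate comparison. Protocol 11.4.2.2 closes by carrying the same methods into that stratum, and SAP 1.5 and 1.6 declare no departure from the protocol. Running SAP 2.4.4.2.2 within the stratum follows directly, and the stratum term drops out. If an analyst instead used all patients with a treatment-by-stratum term, Protocol 11.4.2.2 requires the imputation model to contain at least the regression's variables, so the term would enter both models. In simulation these two routes agreed to about 0.1 point. Only pooled main-effects imputation is harmful, and it fits neither route.

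**5. Size if the harmful route were taken.** Assumed: 0.30 × 140 = 42 usual-care fenofibrate patients; TG change -6% on alirocumab and -25% on fenofibrate; 0, -5, -15 and -15% on no LMT, ezetimibe, omega-3 and nicotinic acid; 10% missing. The robust estimate of the gap is about 17.6 points, in favour of fenofibrate.
- Week 24 alone missing: loss of 0.2-0.4 against within-stratum imputation. The loss is 0.75 if fenofibrate is set to -35% and the other options to between 0 and -10%.
- Only Week 8 seen: loss of 0.4-0.7.
- The SD of the estimate is about 4.7 pooled and 4.9 within stratum.
- Gap over SD: within stratum 17.6 / 4.9 = 3.59. Pooled, with the 0.75 loss, (17.6 - 0.75) / 4.7 = 3.59. The two-sided 0.025 threshold is 2.24.

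The small bias and the smaller spread offset each other, and the sign does not change.

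**The case for a change.** The best argument for a change is pre-specification. In an open-label trial, a confirmatory test should not admit two programs. The protocol's closing sentence is printed under Binary endpoints, so its reach to TGs and Lp(a) is a matter of reading. The parallel protocol sentence for the primary endpoint also spoke of the stratum, yet SAP 2.4.4.1.1 replaced it with an all-patient interaction model and kept within-stratum fitting only as a fallback. An analyst could therefore ask which approach governs TGs. A sentence in each of two SAP sections would settle everything.

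It stands that the wording is incomplete and that the clarification would be harmless. It does not stand that the results are at risk, because the two legitimate readings agree to about 0.1 point. Larger shifts can be produced. One simulation of the fenofibrate contrast reached 3.7 points, but it needed 15% missing, a 30-point difference in treatment effect between strata, a 20% stratum share and no other visit observed. With Weeks 8-20 observed the shift was at most about 0.8. The no-other-visit case is nearly closed off: the ITT population requires a post-baseline non-HDL-C value, and TGs come from the same lipid panel. Nor should fasting rules open many TG gaps, since Protocol section 10 has non-fasting patients rebooked rather than sampled.

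The suggested additions also leave discretion. Strata would have to be pooled where sparse, without a rule; at an assumed 5% share, nicotinic acid has 0.05 × 140 = 7 usual-care patients.

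**Conclusion.** No change follows. The omissions are real but are details that competent analysts would fill in the same way: by-arm imputation in the pattern-mixture analysis, and imputation and robust regression within the fenofibrate stratum (or with the interaction in both models) for TGs and Lp(a). On that reading, the missing baseline and stratum terms are worth about 0.1 point on a difference near -29 when missingness is alike in both arms, and up to about 0.9 in the most unfavourable one-sided case. For the fenofibrate TG contrast, even the unsuitable pooled imputation costs 0.2 to 0.75 points out of about 17.6 at 10% missing with only Week 24 absent. A shift of 0.75 / 4.9 = 0.15 SD could matter only for a result lying almost exactly on the threshold. No bias has been shown for Lp(a). All magnitudes rest on assumed effects, SDs, correlations, stratum shares and missing rates, since the public documents give none. The conclusion would weaken if on-treatment gaps far exceeded 20%, or if the pattern-mixture model were in fact fitted pooled without treatment, which the arm-specific text does not call for.

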## Subgroups of interest are:

- Gender: Female, Male;
- Menopausal status, for female only: Yes, No;
  - For post-menopausal women, type of hormone replacement therapy: estrogen only, estrogen and progesterone, no estrogen or progesterone;
- Age: <65, [65 75[ and  $\ge 75$  years; 65,  $\ge 65$  years old;
- BMI: <25, [25-30],  $\ge 30$  in kg/m2;
- Race: White/Caucasian, non-White/Caucasian;
- Ethnicity: Hispanic or Latino, non-Hispanic or Latino, Not reported/Unknown;
- Region (North America, Europe, Rest of World);
- Duration of diabetes: <5, [5-10], >10 years, if the number of patients by subgroup are sufficient; otherwise by tertiles;
  - o Patients with duration of diabetes < 1 year are excluded.
- Prior history of myocardial infarction (silent or acute) or ischemic stroke: Yes, No;
- CKD: Yes, No, from cardiovascular medical history e-CRF page;
- ASCVD as per protocol (see Section 2.1.1): Yes, No;
- ASCVD including TIA (see Section 2.1.1): Yes, No;
- eGFR: <30,[30 60[, [60 90[,  $\ge$ 90 mL/min/1.73m^2, if there are not enough patients with eGFR <30, the <30 and the [30-60] categories will be pooled together;
- Baseline albumin/creatinine ratio: <30, [30 300[,  $\ge 300$  mg/g (<3.39, [3.39-33.9[,  $\ge 33.9$  mg/mmol);
- Diabetic kidney disease by category (cf Appendix C)
  - o Category 1: (G1A1, G2A1)

26-Apr-2017

- o Category 2: (G1A2, G2A2, G3aA1)
- o Category 3: (G1A3, G2A3, G3aA2, G3bA1)
- o Category 4: (G3aA3, G3bA2, G3bA3, G4A1, G4A2)
- o Category 5: (G4A3, G5A1, G5A2, G5A3)

If the numbers of patients by subgroup don't allow this subgroup analysis, other groupings will be explored.

- Baseline total PCSK9 level: <median, ≥median;
- Baseline free PCSK9 level: <median, ≥median;

- Baseline HbA1C:
  - $\circ$  <7, [7 − 9[, ≥9%. if the number of patients by subgroup meets the requirement (cf. above); otherwise <median, ≥median and by tertiles;
  - o Controlled DM (HbA1C<7%) vs uncontrolled DM (HbA1C≥7%)
- Statin treatment at randomization:
  - o Any statin versus no statin
  - o High intensity statin versus medium or low intensity statin at randomization
- Baseline non-HDL-C: <130, [130 160[, [160 190[,  $\ge 190$  mg/dL (<3.37, [3.37 4.14[, [4.14 4.91[,  $\ge 4.91$  mmol/L), ), if the number of patients by subgroup meets the requirement (cf. above); otherwise one of the following groupings will be explored:
  - $\circ$  <130, [130-160],  $\geq$ 160 mg/dL (<3.37, [3.37 4.14],  $\geq$ 4.14 mmol/L)
  - o by tertiles (only if no sufficient patients in previous grouping)

For this specific subgroup factor, the MMRM model will include fixed categorical effects for treatment group, randomization stratum as per IVRS, baseline non-HDL-C category, time point, and the interactions treatment group-by-time point, stratum-by-time point, baseline non-HDL-C category-by-time point, treatment group-by-baseline non-HDL-C category, and treatment group-by-baseline non-HDL-C category-by-time point;

- Baseline calculated LDL-C: <100, [100 130[, [130 160[,  $\ge 160$  mg/dL (<2.59, [2.59 3.37[, [3.37 4.14[,  $\ge 4.14$  mmol/L), if the number of patients by subgroup meets the requirement (cf. above); otherwise one of the following groupings will be explored:
  - $\circ$  <100, [100-130],  $\geq$ 130 mg/dL (<2.59, [2.59 3.37],  $\geq$ 3.37 mmol/L)
  - o by tertiles (only if no sufficient patients in previous grouping)
- Baseline HDL-C: low HDL-C (<40 mg/dL (<1.04 mmol/L) for males / <50 mg/dL (<1.29 mmol/L) for females), high HDL-C ≥40 mg/dL (≥1.04 mmol/L) for males / ≥50 mg/dL (≥1.29 mmol/L) for females);

- Baseline TGRL:
  - $\circ$  <30,  $\geq$  30 mg/dL
  - o by quintiles
- Baseline fasting TG:
  - $\circ$  <150, [150 200],  $\geq$ 200 mg/dL (<1.7, [1.7 2.3],  $\geq$ 2.3 mmol/L);

- $\circ$  <150,  $\geq$ 150 mg/dL (<1.7,  $\geq$ 1.7 mmol/L);
- o by quintiles;
- Baseline Lp(a):
  - $\circ$  <30, [30 50[,  $\geq$ 50 mg/dL (<0.3, [0.3 0.5[,  $\geq$ 0.5 g/L);
  - $\circ$  <30,  $\geq$ 30 mg/dL (<0.3,  $\geq$ 0.3 g/L);

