#### 8.8 CONCOMITANT MEDICATION

A concomitant medication is any treatment received by the patient concomitantly to any IMP(s) during the study, until Week 32. This medication is not provided by the Sponsor.

Concomitant medications should be kept to a minimum during the study. However, if these are considered necessary for the patient's welfare and are unlikely to interfere with the IMP, they may be given at the discretion of the Investigator, with a stable dose (when possible). Besides the specific information related to concomitant medications provided in this section, any other concomitant medication(s) will be allowed and will have to be recorded in the e-CRF and source data.

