# Other baseline characteristics

- Female menopausal status:
  - o occurrence
  - for postmenopausal women, time since menopause (years), menopausal symptoms controlled status and type of hormone replacement therapy (estrogen only, estrogen and progesterone, no estrogen or progesterone)
    - The type of hormone replacement therapy will be obtained from concomitant treatments.
- Lipid efficacy parameters:
  - o Non-HDL-C, quantitative and by category: <100, [100 130[, [130 160[, [160 190[, [190 220[, >220 mg/dL (<2.59, [2.59 3.36[, [3.36 4.14[, [4.14 4.91[, [4.91 5.70[, ≥5.70 mmol/L)]
  - Calculated and measured LDL-C, quantitative and by category: <70, [70-100[, [100-130[, [130-160[, [160-190[,  $\ge 190 \text{ mg/dL}$  (<1.81, [1.81-2.59,[] [2.59-3.37[, [3.37-4.14[, [4.14-4.91[,  $\ge 4.91 \text{ mmol/L})$
  - $\circ$  Apo B, quantitative and by category:  $<80, \ge 80 \text{ mg/dL}$  ( $<0.8 \text{ g/L}, \ge 0.8 \text{ g/L}$ )
  - Lp(a), quantitative and by category: <30, [30 50[,  $\ge 50$  mg/dL (<0.3, [0.3 0.5[,  $\ge 0.5$  g/L); <30,  $\ge 30$  mg/dL (<0.3,  $\ge 0.3$  g/L)
  - HDL-C, quantitative and by category: <40,  $\ge40$  mg/dL (<1.04,  $\ge1.04$  mmol/L) for men /<50,  $\ge50$  mg/dL (<1.29,  $\ge1.29$  mmol/L) for women
  - Fasting TGs, quantitative and by category: <150, [150 200[,  $\ge 200 \text{ mg/dL}$  (<1.7, [1.7 2.3[,  $\ge 2.3 \text{ mmol/L}$ ); <150,  $\ge 150 \text{ mg/dL}$  (<1.7,  $\ge 1.7 \text{ mmol/L}$ )
  - o TGRL, quantitative and by category:  $< 30, \ge 30 \text{ mg/dL}$  ( $< 0.3, \ge 0.3 \text{ g/L}$ )
  - All other quantitative lipid efficacy parameters (Total-C, Apo A-1, Apo C-III, ratio Apo B/Apo A-1, ratio Total-C/HDL-C, ratio LDL-C/HDL-C, LDL particle number and size, VLDL, HDL, IDL particle number)
- Metabolic parameters:
  - o Glycated hemoglobin A1c (HbA1c), quantitative (%, mmol/mol) and by category: <7, [7 9[, ≥9 %; <7, ≥7 %; <8, ≥8 %; <9, ≥9 %

26-Apr-2017

Fasting plasma glucose (FPG), quantitative variable (mg/dL and mmol/L)

26-Apr-2017

Version number: Final

- Total and free PCSK9 levels as quantitative (ng/mL)
- eGFR, quantitative and by category: [15 30], [30 60], [60 90],  $\ge 90$  ml/min/1.73 m^2
- Albumin/creatinine ratio, quantitative and by category: < 30, [30 300[,  $\ge 300 \text{ mg/g}$  (< 3.39, [3.39 33.9[,  $\ge 33.9 \text{ mg/mmol})$ ;
- Diabetic kidney disease category defined below (cf. Appendix C) (7):
  - o Category 1: G1A1, G2A1
  - o Category 2: G1A2, G2A2, G3aA1

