#### 2.1.2 Prior or concomitant medications

All medications taken within 3 months before screening visit and until the end of the study are to be reported in one of the following specific e-CRF pages:

- Cardiovascular Drugs
- Lipid Modifying Therapy (Including Statin) and Nutraceutical Products that May Affect Lipids
- Other Drugs

All medications will be coded using the World Health Organization-Drug Dictionary (WHO-DD) using the version currently in effect at Sanofi at the time of database lock.

- Prior medications are those the patient used within 12 weeks prior to screening visit and prior to first dose of open-label alirocumab injection/first dose of usual care treatment for those prescribed another LMT if allocated to the usual care arm. For those allocated to the usual care arm and for whom no other LMT is prescribed, the pre-treatment period will end on the day before randomization. Prior medications can be discontinued before first administration or can be ongoing during treatment phase.
- Medications taken at baseline are those the patient started before or on the day of the first dose of open-label alirocumab injection/first dose of usual care treatment (for those prescribed another LMT in the usual care arm)/randomization (for those not prescribed another LMT in the usual care arm), and ongoing or ended on or after the day of the first dose of open-label alirocumab injection/first dose of usual care treatment (for those prescribed another LMT in the usual care arm)/randomization (for those not prescribed another LMT in the usual care arm).

- Concomitant medications are any treatments received by the patient from first dose of open-label alirocumab injection to the last dose of open-label treatment + 70 days (10 weeks). For patients randomized to usual care, this will be considered as 70 days after the last dose of usual care treatment has been administered, or Study Day 225, whichever comes first. For patients randomized to usual care arm without additional LMT prescribed, the "date of last dose of usual care" is defined as the date of the last on-site visit. A given medication can be classified both as a prior medication and as a concomitant medication. Concomitant medications do not include medications started during the post-treatment period (as defined in the observation period in Section 2.1.4).

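### Type of hormone replacement therapy is treated as a baseline characteristic and subgroup factor, but its stated source also takes in therapy first started after randomization

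*SAP*

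**What the plan says.** Three parts of the SAP bear on this variable.

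- **SAP 2.4.4.1.3, subgroup list.** A factor nested under menopausal status reads "For post-menopausal women, type of hormone replacement therapy: estrogen only, estrogen and progesterone, no estrogen or progesterone". It carries no time anchor.
- **SAP 2.1.1.** Under the heading "Other baseline characteristics", the same three categories are listed for postmenopausal women, with one line on derivation: "The type of hormone replacement therapy will be obtained from concomitant treatments".
- **SAP 2.1.2.** "Concomitant medications are any treatments received by the patient from first dose of open-label alirocumab injection to the last dose of open-label treatment" plus 70 days. For usual care the period is capped at Study Day 225. The only exclusion by start date is this: "Concomitant medications do not include medications started during the post-treatment period". The same section defines a different category that is not used for hormone therapy: "Medications taken at baseline are those the patient started before or on the day of the first dose of open-label alirocumab" or of usual care (or randomization, for patients given no additional lipid-modifying therapy), and not ended before that day.

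Protocol 8.8 is about as broad: "A concomitant medication is any treatment received by the patient concomitantly to any IMP(s) during the study, until Week 32".

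**The concern.** A factor used to examine whether the treatment effect is homogeneous should be fixed before treatment starts, and a baseline table should show what patients were taking at baseline. The stated source meets neither requirement for a woman whose hormone therapy begins or is extended during the study. Protocol inclusion criterion I 08 names estrogen replacement among drugs known to influence weight and/or lipids, so the variable was presumably chosen because it may relate to the outcome. I 08 requires stability only up to the end of screening. After randomization, Protocol 8.8 lets the investigator give other concomitant drugs, and hormone therapy is not on the prohibited list in Protocol 8.8.3.

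At stake are the accuracy of one baseline row and the interpretability of one line in the subgroup forest plot.

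**Working it through.** There is no planned figure to reproduce. The check sets the definitions side by side and then considers scale.

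**1. How far the concomitant window reaches.** The last planned injection is at Week 22, which is Day 1 + 22 × 7 = Day 155. Adding 70 days gives Day 225. The Week 24 visit is Day 169. SAP 2.1.4 starts the post-treatment period the day after the treatment-emergent period ends. So for a patient who completes alirocumab on schedule, a drug first taken at any time from Day 2 to Day 225 is concomitant, including one started after the Week 24 efficacy sample. SAP 2.5.2 adds that a medication whose dates do not show whether it was prior or concomitant is counted as both.

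**2. What the concomitant category adds.** Therapy that meets the SAP's baseline-medication definition is being taken on or after the day of first dose, so it is also concomitant. What the broader category adds is therapy started later, which should not define a baseline variable.

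**3. Which women move category under the literal rule.**

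| Hormone therapy after randomization | Literal classification | Correct at baseline? |
|---|---|---|
| Unchanged since before randomization | Same type | Yes |
| Dose, brand or route changed | Same type | Yes |
| Stopped, or one of two hormones dropped | Original type, since it was still taken after first dose | Yes |
| First started | User category instead of none | No |
| Second hormone added | Both hormones instead of one | No |

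Only the last two rows are affected.

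**4. Comparison with similar variables.** The statin subgroup factor is fixed at randomization, SAP 2.4.2 describes lipid-modifying therapies at randomization, and the same section tabulates glucose-lowering treatments at baseline and, separately, at Weeks 12 and 24. Hormone therapy type has no such anchor.

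**5. Scale.** The subgroup rule needs at least 10 patients per subgroup and arm. With 140 patients in usual care and 280 on alirocumab, a category must hold at least 10/140 = 7.1% and 10/280 = 3.6% of the respective arm. Smaller categories are pooled if possible or excluded.

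The documents give no sex ratio, menopausal share, hormone-therapy prevalence or starting rate, so the following is assumption only. If a user category held 1% to 5% of usual care, that is 1.4 to 7 women, below the minimum. If there were 160 postmenopausal women in the trial and 1% to 3% started or added a hormone, 160 × 0.01 = 1.6 to 160 × 0.03 = 4.8 women would move. At 2:1 allocation about a third of them, 0.5 to 1.6, would be in usual care. Such numbers could decide whether a category is analysed only if it already stood just below 10.

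**The case against.** The best defence is that the line in SAP 2.1.1 names a data source and leaves timing to the surrounding text. It sits under a baseline heading, and SAP 2.1 opens by defining baseline in general as the last assessment before first dose or randomization. The line says treatments, not medications, and does not cite SAP 2.1.2. The protocol also has concomitant medication recorded at screening and at the randomization visit, so the phrase could simply point to those records. This is plausible as to intent, and a baseline value probably was intended. It does not remove the ambiguity: the only defined concomitant category is the broad one, and no text restricts hormone therapy type to treatment ongoing at randomization.

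A reader might also infer something stronger: that the subgroup is in effect defined by post-randomization data, that every change in hormone therapy misclassifies a woman, or that membership will depend on treatment arm. The documents do not support this.

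- Therapy continuing from before randomization is concomitant too, and is classified correctly. Stops and dose changes move nobody.
- Arm-dependent prescribing is possible in an open-label trial, but nothing in the documents suggests why knowing the arm would alter menopausal hormone prescribing. Central-laboratory lipid results after randomization are withheld from sites (apart from triglyceride alerts), and Protocol 8.8 asks that concomitant drugs be kept to a minimum.
- The subgroup interaction result is labelled descriptive.

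**Conclusion.** The point holds as a minor defect of definition, located in SAP 2.1.1; the subgroup list inherits it. Applied literally, the rule can place a woman who starts or extends hormone therapy after randomization in the wrong row of the baseline table and the wrong subgroup. Very few women are likely to be affected, but that is a judgement, since the documents supply no rate. User categories may well be too small to be analysed separately; the baseline table has no minimum size, so the error could still show there. The primary and key secondary analyses do not use this variable.

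**What to change.** In SAP 2.1.1, replace the derivation line with: *the type of hormone replacement therapy will be obtained from medications ongoing at randomization*. In 2.4.4.1.3, state that this same classification defines the subgroup.

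Randomization is a cleaner anchor than first dose. Usual care treatment may start up to 7 days after randomization, whereas the first alirocumab injection is given at the randomization visit, so a first-dose anchor would leave a short post-randomization gap in one arm only. Randomization is also the anchor already used for statins.

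The cost is a few words of SAP text. It needs no new data, because the SAP's medication categories already rely on start and stop dates.
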